6.1.6.1.2 CHQ-PF50

[Appendix 5](#) describes the methods of handling missing data for the CHQ-PF50 health scales.

6.1.6.1.3 Adverse Events

Missing and/or incomplete dates for AEs will be imputed in a manner resulting in the earliest onset or the longest duration during the treatment period, while ensuring that the start date is not after the stop date, i.e. missing start dates will be imputed as the first day of the month/first month of the year and missing stop dates will be imputed as the last day of the month/last day of the year, while ensuring that the start date is not after the stop date. Upper and lower limits of imputation will be date of Visit 1 and last visit date as defined in [section 6.1.3](#), and events occurring on date of Visit 1 will be assumed post-IMP. Stop dates will not be imputed if the AE is ongoing.

Imputed dates will be used for calculation of time to first onset and time to AE resolution, they will not be presented in AE listings.

A worst-case approach will be followed in the event of missing severity or causality data. If the

severity is missing, 'Severe' will be imputed. If causality data is missing for a treatment emergent AE (TEAE), 'Yes' will be imputed for the question 'Plausible relationship to study medication'.

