9.1 Trial Procedures by Visit

Patients and their parent(s)/legal representative will be invited to take part in the trial and will be issued with the patient information and informed assent (if applicable) and the parent(s)/legal representative information and informed consent. Due to the degree of cognitive impairment in patients with RTT, patients 18 years of age or older will not be required to provide consent and will only be required to provide assent in cases where the patient possesses adequate understanding, along with parent(s)/legal representative consent. Following ample time to discuss the trial with the investigator, nurse, relatives, or caregiver, as wished, patients for whom the parent(s)/legal representatives provide written informed consent, and in cases where the patient possesses adequate understanding, patients who give their assent will be screened for entry into the trial. The nominated caregiver will be asked to consent to complete the QoL questionnaires.

Each visit should be scheduled to take place at approximately the same time of day (i.e., morning or afternoon), whenever possible. Visits 2, 3, and 16 (safety follow-up) are to be conducted by telephone.

The investigator should use his/her judgment and knowledge of the patient to determine when to best collect the blood and urine samples in order to mitigate the risk that invasive procedures may cause the patient to become stressed, thereby affecting the results of other patient assessments.

All assessments should reflect the patient's regular state, therefore it should be ensured the patient had adequate time to settle prior to each assessment. The CGI-S and CGI-I assessments should be based on the entirety of the visit.

Study Code: GWND19002
EudraCT Number: 2019-001605-24
Clinical Protocol V2 18Dec19

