9.2.15 Adverse Events

All AEs (including SAEs) occurring during the trial will be reported on the running logs in the AE section of the eCRF. This includes all events from the time following screening (Visit 1) up to and including the post-trial follow-up visit (Visit 16), whether or not attributed to GWP42003-P and observed by the investigator or patient.

* For the patient's expected seizure types, these do not routinely require documentation as AEs. However, any worsening, including a change in the pattern or severity of seizures should be documented in the eCRF if deemed to meet the definition of an AE, in the investigator's opinion.

Study Code: GWND19002
EudraCT Number: 2019-001605-24
Clinical Protocol V2 18Dec19

Any AE that meets SAE criteria should still be reported as a SAE.

Serious adverse events must be reported to GW Pharmacovigilance Department (PVD) within 24 hours of discovery or notification of the event via recording in the eCRF.

Refer to [Section 12](#) for definitions, procedures, and further information on AE reporting.

Study Code: GWND19002
 EudraCT Number: 2019-001605-24
 Clinical Protocol V2 18Dec19

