12.6 Reporting Procedures for All Adverse Events

All AEs (including SAEs) occurring during the trial will be reported on the running logs in the AE section of the eCRF. This includes all events from the time following screening (Visit 1) up to and including the post-trial safety follow-up visit (Visit 16), whether or not attributed to GWP42003-P and observed by the investigator or patient.

For the patient's expected seizure types, these do not routinely require documentation as AEs. However, any worsening, including a change in the pattern or severity of seizures, should be documented in the CRF if deemed to meet the definition of an AE, in the investigator's opinion.

Any AE that meets the SAE criteria should still be reported as an SAE.

The following information will need to be provided for all AEs:

A) Adverse Event (Diagnosis or Syndrome, if Known, or Signs and Symptoms)

Where the investigator cannot determine a diagnosis, signs or symptoms should be recorded in the AE section of the eCRF. Once a diagnosis has been determined, the AE section of the eCRF must be updated to reflect the diagnosis in replacement of the original symptoms. In circumstances where only a provisional diagnosis is possible (working diagnosis), the eCRF must be updated to reflect the provisional diagnosis in replacement of the original symptoms. In some circumstances, it may be relevant for the investigator to include the symptoms alongside the diagnosis in the verbatim event

Study Code: GWND19002
EudraCT Number: 2019-001605-24
Clinical Protocol V2 18Dec19

description. However, the diagnosis (full or provisional) should be clearly stated, e.g., fever and malaise due to respiratory tract infection.

B) Adverse Event Start Date and Stop Date

The start and stop dates of the event must be provided. All AEs require these fields to be completed in full. Partial dates or missing dates are not normally acceptable, and significant effort must be undertaken to obtain any unknown information. If a precise date is not known, an estimated date should be provided instead. When a complete date cannot be given, record as much information as possible (i.e., the month and year or, in exceptional circumstances, just the year). When the actual start date becomes known, the eCRF must be updated to replace the previously recorded date.

C) Outcome

The outcome of the event must be recorded accurately and classified into one of the following categories:

- Recovered
- Recovered with sequelae

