6.1.3 Last Visit

The last visit for endpoints assessed at clinic visits is defined as the last scheduled visit at which a patient's last evaluation (up to Visit 15/end of treatment visit/any other last visit) is performed.

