6.1.6.1.4 Concomitant Medication

Missing concomitant medication dates will be handled in a similar fashion as described for AEs in [Section 6.1.6.1.3](#).

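### Imputed adverse-event dates are capped at a clinic-visit limit that names Visit 15, although events are collected to the Visit 16 call, so partial stop dates in follow-up give shortened durations

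*SAP*

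**What the plan says.** - **The limits.** SAP 6.1.6.1.3 imputes a missing start as the first day of the month (or first month of the year) and a missing stop as the last day of the month or year. The start may not fall after the stop. It then bounds both: "Upper and lower limits of imputation will be date of Visit 1 and last visit date as defined in" section 6.1.3. The sentence names the limits in reverse order; Visit 1 is plainly the lower one.
- **The definition it borrows.** SAP 6.1.3: "The last visit for endpoints assessed at clinic visits is defined as the last scheduled visit" at which the patient's "last evaluation (up to Visit 15/end of treatment visit/any other last visit) is performed". Visit 16 is not named.
- **Collection period.** Protocol V2 section 12.6 has AEs recorded "up to and including the post-trial safety follow-up visit (Visit 16"); section 9.2.15 agrees. Section 9.1 adds: "Visits 2, 3, and 16 (safety follow-up) are to be conducted by telephone". Under section 9.1.2.2, Visit 16 falls 28 (+7) days after the last dose and exists to pick up AEs that continue or begin once drug has stopped.
- **Which events count.** SAP 6.1.8.1 treats every AE as treatment-emergent except those between the last RCT dose and OLE Visit 1. There is no cut-off at end of treatment.
- **Where imputed dates are used.** According to SAP 6.1.6.1.3, only for time to first onset and time to resolution. They do not appear in AE listings.
- **Concomitant medication.** SAP 6.1.6.1.4: "Missing concomitant medication dates will be handled in a similar fashion as described for AEs in" section 6.1.6.1.3.

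**The concern.** The limit comes from a definition made for a different purpose. AEs are not a clinic-visit endpoint, and their last scheduled collection point is a telephone call. The cap therefore leaves the whole off-drug follow-up outside the range in which an imputed date may lie, although that period is observed on purpose and its events enter the treatment-emergent tables. A complete date in follow-up is used as recorded; a partial date in the same period is pulled back. For stop dates the error runs one way, towards shorter events, in a planned table that belongs to the primary safety objective. For some events the paragraph also gives two instructions that cannot both be followed.

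**Working it through.** **Inputs.** Visit 15 is Day 739 and Visit 16 is Day 767 (Protocol V2 Appendix 1; SAP Tables 1 and 3). Resolution time = stop − start + 1 (SAP 6.1.8.1). Resolution categories are up to 7, 8–14, 15–21, 22–28 and more than 28 days, plus ongoing (SAP 9.1).

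**1. Window outside the cap.** The plan's own figure reproduces: 739 + 28 = 767. The window is 767 − 739 = 28 days, or 28 + 7 = 35 with the Visit 16 window.

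**2. Onset on drug, partial stop in follow-up.** Take Visit 15 on 20 January and Visit 16 on 17 February. An AE starts 10 January, its stop is recorded as February, and it truly ends 10 February.
- True duration: 22 + 10 = 32 days (more than 4 weeks).
- Capped at Visit 15: 20 − 10 + 1 = 11 days (2 weeks).
- Limited at Visit 16: 22 + 17 = 39 days (more than 4 weeks).

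**3. Known onset after Visit 15, partial stop.** Same visits, onset 25 January, stop recorded as February. The capped stop is 20 January, giving 20 − 25 + 1 = −4 days. This occurs for every such event, because any stop after Visit 15 is capped to a date before the onset. With the limit at Visit 16 the duration is 7 + 17 = 24 days.

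**4. Typical size.** The rules were applied to 100,000 simulated events per scenario. The assumptions are not from the documents: Day 1 uniform over a year, event dates uniform over a 28-day follow-up, only month and year known, on-drug events starting 0–14 days before Visit 15.

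| Partial stop in follow-up, on-drug onset | Limit at Visit 15 | Limit at Visit 16 |
|---|---|---|
| Mean error in duration | −14.5 days | +9.2 days |
| Moved to a shorter category | 89% | 0% |

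With Visit 15 at Day 67, 180 or 339 (early withdrawal) the left column is essentially unchanged (88–89%). These percentages apply only to events that already have a partial stop in follow-up, and they depend on the assumed onset. An event starting 28 or more days before Visit 15 has a capped duration of at least 29 days and stays in the longest category.

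**5. Start dates.** Every follow-up event with a month-only start is imputed on or before Visit 15. About 52% get there through the first-of-month rule and 48% through the cap. A wrong onset category arises in:

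| Visit 15 at | Limit at Visit 15 | Limit at Visit 16 |
|---|---|---|
| Day 739 | 0% | 0% |
| Day 67 | 49.6% | 47.2% |
| Day 180 | 49.0% | 49.0% |
| Day 339 | 28.6% | 24.4% |

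The cap itself adds at most 28.6 − 24.4 = 4.2 percentage points. For completers nothing changes, since all follow-up onsets lie beyond Day 359, the start of the last category.

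**The case against.** The best defence is textual. The imputation paragraph ties its aim of earliest onset or longest duration to the treatment period, which fits a limit near the end of dosing. SAP 6.1.3 also ends with a catch-all for any other last visit, and Visit 16 is a numbered, scheduled visit. Both points make the text ambiguous; neither settles it. The treatment-period wording sits badly with a treatment-emergent definition that has no end-of-treatment cut-off. The catch-all follows an explicit restriction to clinic visits and an explicit Visit 15. Two programmers could produce different tables.

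Several stronger readings are tempting and are not supported:
- **Negative durations will be printed.** The paragraph requires the start not to be after the stop. What is missing is which rule gives way.
- **Withdrawal events of special interest are re-dated to on-drug days.** SAP 9.1 provides these events as a listing, and imputed dates are not shown in AE listings. No planned AE summary separates on-drug, taper and follow-up time.
- **A patient lost after the Day 15 call has every partial date set to Day 1.** That needs the strictest reading of SAP 6.1.3 and ignores the catch-all.
- **The whole gap to the end of the recorded month is lost.** In step 3 an uncapped month-end stop gives 7 + 28 = 35 days, but the fair comparison, with the limit at Visit 16, is 24.
- **Medication tables are affected.** The rule carries over, but SAP 9.4.1 counts medications by class and preferred term and treats all as concomitant. No output that would change was found.

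Frequency is also a fair objection. Protocol section 12.6 asks for complete or estimated dates and discourages partial ones, and an affected event must also fall in a window of four to five weeks.

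**Conclusion.** The rule is wrong as written, with limited reach. On the natural reading of SAP 6.1.3, an AE with a partial stop date in follow-up loses up to 28 days of duration (35 with the window) and can drop to a shorter resolution category. For a known onset after Visit 15 the paragraph's two instructions conflict, with no precedence stated. The effect on the time-to-onset summary is small, because about half of the shifted starts come from the first-of-month rule and would remain after any change to the cap. Treatment-emergent status, AE counts and listings are untouched, and no hypothesis is tested. The number of affected events cannot be derived from the documents; even if 1–5% of AE records had partial dates, which is only an assumption, only those falling in follow-up would matter. The point is worth correcting because the error in durations runs in one direction and the correction costs almost nothing.

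**What to change.** In SAP 6.1.6.1.3:
1. State that the lower limit is the date of Visit 1 and the upper limit is the date of last contact: Visit 16, or later AE follow-up, death or withdrawal if that is the last contact.
2. Add that an imputed date must stay within the recorded month or year, and that an imputed stop may not precede a known start. Both rules take precedence over the upper limit. The precedence is needed because Protocol sections 9.1.2.2 and 12.7 allow related AEs to be followed beyond Visit 16, so a bare Visit 16 limit could again contradict a recorded month.
3. Say that follow-up is included in the period over which the longest duration is sought, so that the stated aim and the limit agree.

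Keep SAP 6.1.3 for clinic-visit endpoints only. SAP 6.1.6.1.4 inherits the change by reference. The cost is a few sentences and one change in the date-imputation program, with no new data.

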6.1.8.1 Adverse events

Any adverse events occurring between last dose of RCT and OLE visit 1 will not be considered Treatment Emergent Adverse events (Aes occurring during study break). All other adverse events will be considered as treatment-emergent adverse events.

A TEAE will be considered treatment-related if the plausibility relationship to IMP is recorded on the eCRF as 'yes'. If the data on plausibility relationship to IMP is missing then the TEAE will be considered treatment-related.

A TEAE will be considered leading to permanent discontinuation of IMP (leading to withdrawal) if the action taken with IMP is recorded on the eCRF as 'trial medication stopped' or the outcome is recorded on the eCRF as 'patient died'.

A treatment-related TEAEs leading to withdrawal is a TEAE leading to permanent IMP discontinuation and considered treatment-related as per above definition.

A TEAE will be considered leading to IMP temporary discontinuation if the action taken with IMP is recorded on the eCRF as 'trial medication interrupted'.

A TEAE will be considered leading to permanent IMP dose reduction excluding permanent discontinuation if the action taken with IMP is recorded on the eCRF as 'dose reduced'.

A TEAE will be considered fatal if the outcome is recorded on the eCRF as 'patient died'.

The time to first onset of AE will be calculated for TEAEs as:

$$\text{Start date of AE} - \text{Day 1} + 1$$

The time to AE resolution will be calculated for TEAEs as:

$$\text{Stop date of AE} - \text{Start date of AE} + 1$$

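### Imputed adverse-event start dates are floored at OLE Visit 1 even when the recorded month or year ends earlier, and the SAP does not say which date decides the study-break exclusion

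*SAP*

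**What the plan says.** Protocol V2 section 12.6 discourages partial dates but allows them; where a full date cannot be had, sites are to "record as much information as possible (i.e., the month and year or, in exceptional circumstances, just the year").

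SAP 6.1.6.1.3 has four elements that matter here:

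- Partial starts: "missing start dates will be imputed as the first day of the month/first month of the year".
- Bounds: "Upper and lower limits of imputation will be date of Visit 1 and last visit date". In the order given, Visit 1 is paired with the upper limit. It can only be meant as the lower one.
- Timing relative to dosing: "events occurring on date of Visit 1 will be assumed post-IMP".
- A guard, "while ensuring that the start date is not after the stop date", and a stated use: "Imputed dates will be used for calculation of time to first onset and time to AE resolution".

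SAP 6.1.8.1 then defines treatment emergence by exclusion. "Any adverse events occurring between last dose of RCT and OLE visit 1 will not be considered Treatment Emergent Adverse events", and "All other adverse events will be considered as treatment-emergent adverse events".

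**The concern.** A conservative rule is sensible when a partial date leaves it open whether onset was before or after first dose. When the whole recorded month or year lies before Visit 1, nothing is open: onset after Visit 1 is impossible. The floor applies all the same and moves the event to Day 1.

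At stake is the flag behind every TEAE table, which is the core of the primary safety endpoint. If the imputed date feeds that flag, an event from the break between the two trials enters the TEAE tables in the Month 1 onset category (Day 1 to 29, SAP 9.1). That would contradict both the exclusion in SAP 6.1.8.1 and Protocol V2 section 13.6.2.2, which requires onset or worsening after first dose. If its causality were also missing, SAP 6.1.6.1.3 would make it treatment-related. Annex patients, who may have the longest breaks, have their own columns in SAP Table 2, so any error would collect there. It would be hard to see: imputed dates are not shown in the AE listings (6.1.6.1.3), and no data review meeting is planned (4.2.2).

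**Working it through.** The plan states no figure to reproduce, so the rule was applied literally to test dates.

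**Assumed dates (not in the documents):** last RCT dose 20 May 2020, OLE Visit 1 15 September 2020, last visit 31 March 2021.

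**Rule as written:** start = the later of (first day of recorded month or year) and (Visit 1), capped at the last visit.
**Comparison rule:** if the recorded period ends before Visit 1, keep its first day; otherwise floor at Visit 1.
**Day number (SAP 6.1.4):** date − Visit 1 before Visit 1; date − Visit 1 + 1 from Visit 1 on.
**Duration (SAP 6.1.8.1):** stop − start + 1.

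| Recorded start | Stop | As written | Kept in recorded period |
|---|---|---|---|
| Jul 2020 | ongoing | Day 1 | Day −76 |
| Jul 2020 | 20 Oct 2020 | Day 1, duration 36 days | Day −76, duration 112 days |
| Jul 2020 | 10 Aug 2020 | Day 1, duration −35 days: start after stop | Day −76, duration 41 days |
| Sep 2020 | – | Day 1 | Day 1 |
| 2020 only | – | Day 1 | Day 1 |
| 2019 only | – | Day 1 | Day −623 |

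The latest onset consistent with July 2020 is 31 July, 46 days before Visit 1. The third row cannot stand under the SAP's own guard, so a complete stop date in the break should prevent flooring. The first two rows pass the guard. Rows whose recorded period contains Visit 1 are the same under both rules. The 2019 row shows a wrong date but is not a break event on these dates, because it precedes the last RCT dose.

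**How much of a break is exposed.** Suppose onset is uniform over a break of g days and Visit 1 is spread evenly over the 366 days of 2020. The mean number of days of the current month already elapsed at Visit 1 is [7 × 465 + 4 × 435 + 406] / 366 = 5401 / 366 = 14.76. For g of 30 days or more, the share of break days in a calendar month that ends before Visit 1 is 1 − 14.76/g:

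- 38 days: 1 − 14.76/38 = 61%
- 90 days: 1 − 14.76/90 = 84%
- 180 days: 1 − 14.76/180 = 92%

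For shorter breaks a direct count gives 48% at 28 days and 18% at 10 days; same-day entry gives 0%. For year-only dates the counted share is 4% at 28 days and 12% at 90 days. The gap lengths are illustrative. These shares say which break days could be affected if the date were partial, not how many events are.

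**The case against.** The strongest reply is that the imputed date was never meant to decide treatment emergence. SAP 6.1.6.1.3 names time to first onset and time to resolution as the uses of imputed dates. SAP 6.1.8.1 calculates those times for TEAEs, which suggests that status is settled first, and it excludes break events in plain terms. A month lying wholly in the break can be tested against that exclusion without imputation. This stands as far as it goes. A reader might infer that every such event certainly becomes a TEAE; the documents do not support that.

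It does not close the matter. The passage that sets the floor also assigns post-dose status to events on Visit 1, SAP 6.1.8.1 makes TEAE the default, and it never says which date the break test uses. A programmer could follow the text in either direction.

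Three further limits are fair:

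- The guard on start and stop dates protects events with a complete stop date in the break. Events that are ongoing, that stop on or after Visit 1, or that have a partial or missing stop remain exposed.
- A period that ends before Visit 1 need not lie in the break. A year-only date of 2020 with Visit 1 in January 2021 may fall within RCT dosing, so it does not show an off-treatment onset.
- Same-day entry is the recommended route and leaves no break. Protocol V2 section 12.6 also starts OLE event reporting after screening at Visit 1. Events from the break are nevertheless foreseen: AE review is required of everyone at Visit 1, and SAP 6.1.8.1 makes a rule for them.

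**Conclusion.** The concern holds in a limited form. As written, the floor gives a Day 1 onset that the recorded date excludes whenever the recorded month or year ends before Visit 1 and the stop date does not block it. That is a stated rule producing a wrong date, not merely a missing detail. Whether it also produces a false TEAE is conditional: it does so for break events only if the imputed date drives the flag, and the SAP leaves that open.

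The exposure is confined to delayed and annex entrants with partial start dates. The documents give neither the number of partial dates nor the column sizes, so an increase in TEAE percentages cannot be estimated. The count is probably small. The example rests on assumed dates, and the exposure shares on uniform onset and an even spread of Visit 1. Correcting it before programming is worthwhile because it touches the primary safety classification.

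**What to change.** In SAP 6.1.6.1.3, apply the Visit 1 floor only when the recorded month or year contains Visit 1, or when the start is wholly missing and the stop is not before Visit 1. In all other cases impute within the recorded period. Put the limits in the right order, with Visit 1 as the lower and the last visit as the upper.

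In SAP 6.1.8.1, state that the known date parts decide the study-break rule before any imputation.

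The cost is two or three sentences and one programming condition. No new data are needed.
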